Methodology: All necessary factors (clinical, epidemiological, technical, economic, organizational, social, legal and ethical implications) will be considered for the proper implementation of the DHA in healthcare. To

Protocol LANTERN_v1.0 del 16.12.2022

this aim, a robust and rigorous scientific methodology will be applied by combining quantitative approaches (collection of scientific evidence and systematic literature reviews/meta-analysis; consultation of institutional flows and databases/hospital discharge forms/national price lists and data analyses; mathematical models; cost-utility/budget impact analyses) and qualitative research techniques (Consensus conference, Focus group, Delphi, Expert opinion).

The LANTERN project is configured as highly innovative, since for the first time in the field of lung cancer research, we intend to develop a predictive platform powered by the integrated reading of data from the main omics sciences. The project has the ambition to combine data from radiomics with clinical and biological data, derived from biological omics (through the analysis of the patient's biological samples) on a digital platform. This project though seems ambiguous, has a well-thought out plan and is highly feasible through the cooperative work efforts and experience of each consortium partner in their respective fields. With the commitment of each partnering centre in undertaking their respective delegated tasks as described in the project work plans and tasks, We believe the LANTERN project will be completed within a timeframe of 3 years which aligns with the expected time taken for the project completion as stated in the call document.

Personalised medicine represents an evolution from traditional "one size fits all" strategies, extending the concept of stratifying cancer treatments on well-known clinical and pathological characteristics to a more individual, patients specific, truly personalized level. However, the current approach typically relies on molecular and cellular data-sets (i.e. mutations) that are very limited and relative only to subsets of the complex web of cellular data that determine treatment outcomes. Due to various histological, genetic, immunological and imaging characteristics that define its highly variable oncological outcomes, lung cancer represents an ideal case to run AI based multidimensional personalized medicine studies, thereby fitting into the purpose of this project.

AIMS

Main objectives

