The aim of LANTERN project is to develop accurate predictive models for lung cancer patients, using different omics-based variables, integrating well established clinical factors with big data and advanced imaging

features. This technological solution will be able to capture patients' conditions at multiple levels, supporting an effective disease prevention and further reducing the healthcare costs through personalized treatments.

More specifically, we will develop Digital Human Avatars (DHA) defined as computerized representations of individual patients and their characteristics, with a specific focus on advanced biological functions, as well as relevant pathological variables, which will be modelled, sourced and parametrized in a cutting-edge experimental "big data" setting.

Secondary objectives

Our main goals are:

i. To gather information from all the clinical and omics-based data sources acknowledged as clinically significant

ii. To ensure an easy and effective omics data inter-actionability and to allow their complete integration into archiving systems

- iii. To set up dedicated multi-omics data models and create a comprehensive lung cancer DHA
- iv. To enable feedback data loops for preventive healthcare strategies and quality of life (QoL) management
- v. To ensure that all the potential stakeholders are involved in the DHA development process.

METHODOLOGY

This is a prospective observational study

WP1: Omics data collection

The five main omics data tiers that will be identified as the ontology of this project, reflecting all the involved omics domains in the lung-cancer decision making pathway are: A. Demographic and physiological data; B. Medical history, clinic-functional, laboratory data and treatment information; C. Histo-pathological, immunological and genetic data; D. Radiomics and quantitative imaging data; E. Internet of Things derived data.

A structured terminological system for prospective collection of anonymized data will be developed, creating a dedicated database for all omics domains considered. The data will be stored in a dedicated server and categorized according to the data reported in the WP1. Researchers will provide a structured terminological system for prospective collection of anonymized data in which all information will be recorded through specific Case Report Forms (CRFs), ensuring uniformity and consistency for all variables collected. Tumour

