Proposed radiomic analysis will be as follows: first, gross tumour volume (GTV) delineation will be performed retrospectively by experienced lung malignancy Radiotherapy Oncologists on each patient's images (CT images in DICOM (.dcm) format). DICOM files containing not only the CT images but also the RT structure file will be exported and processed using MODDICOM, an R package developed to optimize automatic loading of DICOM images and radiomic analysis. Radiomic features will then be extracted automatically. The extracted radiomic features belong to different families: Intensity-based, morphological, textural and fractal. All analyzed image features will be based on the standardization criteria of the IBSI initiative.

WP3: omics data modelling, avatar creation and knowledge transfer

Developing accurate predictive models and creating Digital Human Avatars (DHA) - Omics features identification and selection: In the first step, an exploratory analysis across all collected datasets (An estimate of \approx 240 NSCLC patients) will enable the start of the biomarker identification process and restrict the cast amount of information towards a more selected pool of potential biomarkers. This first phase will employ robust data analysis techniques in order to identify relevant variables (T3.1.) in a univariate setting, taking individual statistical distributions, feature-relevant correlations and general descriptive statistics into account.

Patient selection

INCLUSION CRITERIA:

- Patients with (suspected) NSCLC
- Age >18 yrs
- ECOG 0-3
- Written Informed Consent

EXCLUSION CRITERIA:

- ECOG 4
- Psychosocial, or emotional conditions controindicating participation to the study

STATISTICAL ANALYSIS METHODOLOGY

An estimate of 600 Patients (both male and female) with \geq 18 years of age with pathologically proven diagnosis of non-small cell lung cancer (NSCLC) will be enrolled. Sample size was calculated on the basis of G-powerR program for "a priori" analysis, considering α =5% and power of 90%.

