The Wilcoxon Mann-Whitney (WMW) test will be used to investigate the ability of these features to predict clinical outcomes on univariate analysis, and the feature showing the lowest p-value will be considered as the most predictive parameter. Receiver Operating Feature curve analysis (ROC) will also be performed on the most significant feature obtained at WMW analysis, calculating the area under the curve (AUC) with the corresponding 95% confidence interval (CI) according to the Clopper-Pearson method. Model processing will be performed through advanced ML and AI techniques first on a dedicated training dataset to fit the model parameters. The obtained hyperparameters will be tuned on a dedicated validation dataset and finally a test dataset will be employed as a dataset independent of the training dataset but following the same probability distribution.

Predictive model development

The objective of the second phase is creating multiple distinct but modular multivariate models, trained through advanced ML and AI techniques and segmented into specific modular areas of interest (T.3.2).

Different supervised models will be developed including logistic regression, decision tree, support vector machine, random forest, XGBoost classifier, and artificial neural networks. The k-fold cross-validation will be used for hyperparameters tuning. The final step in the proposed methodology is the statistical significance comparison of the performance of the ML models. This will be done evaluating predictive performances in terms of different metrics: the first evaluation will be based on accuracy (number of subjects correctly classified on the total number of patients) while the other will be on precision (true positive on total test positive), recall (sensitivity), F1 score (2*precision*recall/(precision+recall)) and AUC-ROC.

We estimate about 300 NSCLC cases with complete data to start developing the models. Specific care will be taken to always ensure both user friendliness and model explainability as primary pillars of the model development strategies. Easily interpretable values such as SHAP (SHapley Additive exPlanations) values will be attached to each model in order to avoid any black-box approaches that might render model outputs, difficult to explain to the patients during their interactions with the clinicians.

Predictive model validation

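### The plan pre-specifies no contrast between the integrated multi-omics model and a reference model of established predictors, so its planned analysis would not show whether integration improves prediction

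*Combined protocol and SAP*

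**What the plan says.** The main objective is to build accurate predictive models by "integrating well established clinical factors with big data and advanced imaging" features. The project rationale argues that "the current approach typically relies on molecular and cellular data-sets (i.e. mutations) that are very limited", and that lung cancer needs a multidimensional approach.

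Under 'Predictive model development', six supervised algorithms are listed: logistic regression, a decision tree, a support vector machine, a random forest, XGBoost and a neural network. The section then gives, as its last step, a "statistical significance comparison of the performance of the ML models". Performance is judged on accuracy first, then on precision, recall, F1 and AUC-ROC. The test is not named. The models are distinguished by algorithm, not by which predictors enter them.

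The same section opens with modular models segmented by area of interest, and it attaches SHAP values to each model. 'Predictive model validation' covers the developed model and the avatar, and looks at robustness, transferability and generalizability. Neither section names a reference model or a measure of incremental value.

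**The concern.** The case for the avatar is that combining data sources predicts better than what clinicians already use. Comparing six algorithms answers a different question, namely which learner fits best. An integrated model may reach a respectable AUC almost entirely through established predictors such as performance status, histology and known mutations. The planned output would look the same whether the added tiers helped or not.

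The validation section ends with the model being applied in routine care. Tumour sequencing, contouring for radiomics and device data all carry a cost. Whoever decides on adoption needs to know what they add to information already at hand.

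**Working it through.** **1. Planned comparisons against the question.**
- 'AIMS' and the rationale: integration of established factors with omics and imaging. The implied question is whether integration improves prediction.
- 'Predictive model development': contrasts among algorithms. No contrast removes the new tiers while the algorithm stays fixed.
- Modular wording (same section) and use of models singly or merged ('ABSTRACT'): these describe structure and use. No module is named as a benchmark.
- SHAP: it divides a prediction among the inputs of one fitted model. It does not say how a model without those inputs would perform.
- 'Predictive model validation': one model and the avatar are assessed, with no comparator.

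The omission is therefore confirmed by the text and depends on no number.

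**2. Does the sample size imply such a comparison?** The plan gives "An estimate of 600 Patients (both male and female"), says "Sample size was calculated on the basis of G-powerR program", and adds only "considering α =5% and power of 90"%. With no effect size or test stated, 600 can be neither reproduced nor refuted. Back-solved for two equal groups with a two-sided test, d = (1.960 + 1.282) × √(2/300) = 0.265. That value appears nowhere in the documents, and nothing links 600 to a model comparison.

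**3. What the missing contrast could deliver.** Assumptions, none from the documents: reference AUC 0.70, integrated AUC 0.75, 30% events, and two independent normal scores of fixed, known form. The evaluation sizes are 420, the plan's figure for starting validation, and 180 = 600 − 420. The 180 is an inference, since no split sizes are given.

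Simulated 95% half-widths of the paired difference are 0.058 (n = 180), 0.037 (n = 420) and 0.031 (n = 600). Power for a true gain of 0.05, two-sided 5%, is Φ(0.05/SE − 1.96) with SE = half-width/1.96:

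| n | SE | 0.05/SE | Power |
|---|---|---|---|
| 180 | 0.0296 | 1.69 | 39% |
| 420 | 0.0189 | 2.65 | 75% |
| 600 | 0.0158 | 3.16 | 89% |

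For comparison, the half-width for the integrated AUC alone is about 0.050 at n = 420 and 0.078 at n = 180. Pairing therefore helps.

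**4. Sensitivity.** Write V1 and V2 for the Hanley–McNeil variances of the two AUCs and r for their correlation. Then SE² = V1 + V2 − 2r√(V1·V2). At n = 420 with 30% events, V1 = 0.000853 and V2 = 0.000767:
- r = 0.3: SE 0.0337, power 32%
- r = 0.5: SE 0.0285, power 42%
- r = 0.7: SE 0.0221, power 62%

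The simulated scores have a correlation of about 0.75, so step 3 sits at the favourable end. Over 20–50% events and r from 0.3 to 0.7, 90% power for 0.70 against 0.75 needs 643 to 2,773 evaluation patients. For 0.70 against 0.80 it needs 153 to 652.

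**5. Number of algorithm contrasts.** Six algorithms give 6 × 5/2 = 15 pairs per metric, or 75 over five metrics. If the 15 tests were independent, the chance of at least one false positive at 5% would be 1 − 0.95^15 = 54%. These tests are in fact correlated, so 54% only indicates scale. None of them addresses the value of integration.

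**The case against.** The strongest reply is that the stated aim is to develop accurate models and avatars. No hypothesis of superiority over established factors is written down, so the plan does not contradict itself. That is correct, and it limits the point to a recommended addition. It does not remove the gap, because accuracy without a reference is hard to interpret.

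Second, the phrase about comparing the ML models could be stretched to cover the modular ones, possibly including a clinical module. The wording leaves room for this but does not plan it.

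Three stronger readings are tempting, and the documents do not support them:
- *The study cannot show added value.* This is true only of the analysis as written. Demographic, clinical and pathological data are collected in the same patients, so the contrast can be computed.
- *The right comparator is clinical factors alone.* The abstract puts actionable mutations and PD-L1 expression in present decision-making, and the rationale describes current practice as relying on mutation data. A reference limited to tiers A and B would credit the avatar with information already in use.
- *420 patients would settle the matter.* Power is about 75% on favourable assumptions and lower on others. Moreover, 420 is the number at which validation starts, spanning cross-validation and external validation, and is not a held-out test set.

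**Conclusion.** The point holds as an omission from the planned analysis. The only significance comparison specified is among the ML models, listed as six algorithms. No contrast with a model of established predictors is pre-specified, so the plan as written would not show whether integration improves prediction. The data to be collected would allow it.

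This conclusion rests on the text alone. The figures for precision rest on assumed AUCs of 0.70 and 0.75, 30% events and fixed scores: half-width about 0.037 and power about 75% at 420, and 0.058 and about 39% at 180. Refitting and feature selection in high-dimensional data would widen these intervals. The change should be made before modelling starts.

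**What to change.** In 'Predictive model development', add:

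1. **A reference model of established factors.** Use tiers A and B plus routine pathology and markers already in use. The abstract names actionable mutations and PD-L1. Stage and histology are suggested here as further routine items, and the investigators should fix the list. A model with tiers A and B only may serve as a secondary reference.
2. **Like-for-like fitting.** Use the same outcome, algorithm class, patients, folds and test data for both models, with any feature selection repeated inside the folds. The outcome must first be named, since the plan refers only to predicting clinical outcomes. AUC as the measure presupposes a binary one.
3. **The main model comparison.** Take the paired difference in AUC, integrated minus reference, with a 95% confidence interval (DeLong or bootstrap). State the gain regarded as worthwhile and the size of the evaluation set.
4. **Algorithm contrasts.** Report the 15 pairs per metric as descriptive, or adjust them by Holm's method.

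The cost is one further model on data already collected and a short paragraph of text. The drawback is limited precision. The interval should carry the interpretation, with an explicit statement that a non-significant difference does not show that omics adds nothing.

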Both the developed model and the comprehensive DHA will be validated in order to test their robustness, transferability and generalizability. Two consecutive validation strategies will be employed respectively: the internal and external validation techniques. We estimate a total number of \approx 420 NSCLC cases to start the validation process. This process will include both internal and external validation. The internal validation step will be focused mainly on techniques such as K-fold cross validation. This will allow to achieve a Transparent Reporting of a multivariable prediction model for Individual Prognosis Or Diagnosis (TRIPOD) level 2b. At this TRIPOD level, data are non-randomly split (e.g., by location or time) into 2 groups: one to develop the prediction model and the remaining dataset to evaluate its predictive performance. In the case of suboptimal performances, all the failing models will be reverted back to the previous stage and the models will be retrained with new specifications in order to increase their robustness. At this point, the models can be validated using external datasets, reaching TRIPOD 3 and 4 levels (External validation). Finally, when the models reach a TRIPOD 4 level, data transferability and full actionability will be granted, allowing the successful and safe application of the model in the clinical Routine (T3.3).

ETHICAL CONSIDERATIONS

Considering the technicality and complexity of the LATERN Project, consortium partners are well aware of the various ethical and legal questions relating to the project. The main ethical issues related to this project include:

the respect for persons and for human dignity; fair distribution of benefits and burden; the rights and interests of the participants; the need to ensure participants' informed consent; processing of personal data; concerns involving the development, deployment and/or use of artificial intelligence (AI)-based systems or techniques.

Protocol LANTERN_v1.0 del 16.12.2022

Therefore, LATERN partners will identify and implement a comprehensive set of ethical and legal requirements in accordance with Declaration of Helsinki principles to ensure compliance for all activities of the project. Appropriate ethical monitoring systems will also be set up.

To this effect, LATERN will implement the following activities:

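### No calibration measure is planned for models meant to describe individual patients, and accuracy comes first among the metrics with no outcome rate, cut-off or deciding metric stated

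*Combined protocol and SAP*

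**What the plan says.** Predictive model development (protocol, under Statistical analysis methodology) trains six supervised algorithms, from logistic regression to neural networks, and tunes them by cross-validation. It then states: "The final step in the proposed methodology is the statistical significance comparison of the performance of the ML models". Of the metrics, "the first evaluation will be based on accuracy", defined as the share of patients correctly classified. A second group follows: precision, recall, "F1 score (2*precision*recall/(precision+recall)) and AUC-ROC". The section does not name the outcome, its expected rate, the probability cut-off used for classification, or the metric that decides between models.

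Predictive model validation says that the model and the avatar "will be validated in order to test their robustness, transferability and generalizability", by internal and then external validation. Models that perform below expectation go back for retraining, but no metric or threshold defines this. Neither section, nor any other, mentions a calibration plot, intercept or slope, or a Brier score.

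The intended use is at patient level. Main objectives defines the avatars as "computerized representations of individual patients and their characteristics". The validation section ends with models that have passed external validation, "allowing the successful and safe application of the model in the clinical Routine".

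**The concern.** Accuracy, precision, recall and F1 use only which side of a cut-off a patient falls on. AUC uses only the ranking of patients. None of them uses the size of the predicted risk. If a clinician or patient is shown an individual risk, its size is what matters, and the plan has no step that would show it to be wrong. Overconfident predictions are a usual result of fitting flexible algorithms to a modest sample, and the plan expects to start development with about 300 complete cases.

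The second issue is the place given to accuracy. With an unbalanced outcome, a rule that assigns everyone to the commoner class already has high accuracy, so a model with real discrimination may hardly exceed it. Without a stated outcome rate, cut-off or deciding metric, the reader cannot tell whether this applies, and the choice of metric stays open until results are seen.

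**Working it through.** The plan gives no performance figure to reproduce, so the check asks what the five listed metrics can detect.

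**Inputs from the protocol:** the five metrics, and about 420 cases at the start of validation. **Assumptions:** event rate p of 10% to 40%, AUC 0.75, cut-off 0.5, equal-variance binormal scores, and all 420 cases used as one test set.

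**Formulas.** Separation d = √2 × Φ⁻¹(AUC) = √2 × Φ⁻¹(0.75) = 0.954. For a calibrated model, risk 0.5 lies at score c = (d²/2 − logit p)/d. Recall = Φ(d − c), specificity = Φ(c), accuracy = p × recall + (1 − p) × specificity.

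**Step 1: calibrated model at 20% events.** c = (0.455 + 1.386)/0.954 = 1.930. Recall = Φ(−0.976) = 0.164 and specificity = Φ(1.930) = 0.973. Accuracy = 0.0329 + 0.7786 = 81.15%. True positives are 0.0329 and false positives 0.0214 of all patients, so precision = 0.0329/0.0543 = 0.61 (0.604 in the simulation below).

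**Step 2: the same model made overconfident.** Double every logit (calibration slope 0.5). A logit keeps its sign, so each patient stays on the same side of 0.5 and accuracy, precision, recall and F1 cannot change. The ranking is also unchanged, so AUC cannot change. A simulation of 400,000 patients gives:

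| 20% events | Calibrated | Logits doubled |
|---|---|---|
| Accuracy | 81.2% | 81.2% |
| Precision | 0.604 | 0.604 |
| Recall | 0.164 | 0.164 |
| AUC | 0.751 | 0.751 |
| Mean predicted risk (observed 20.0%) | 20.0% | 11.0% |
| Brier score | 0.137 | 0.148 |

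The overconfident model places about 71% of patients below 10% risk. Their mean predicted risk is 2.6% and their observed rate is about 12%. At 10% and 30% events the listed metrics again agree, while mean predicted risk is 3.0% and 22.4% against 10% and 30% observed.

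**Step 3: accuracy against the majority-class rule.** The gain equals true positives minus false positives (TP − FP, as shares of all patients). The paired 95% half-width is 1.96 × √{[TP + FP − (TP − FP)²]/n}. At 20% events and n = 420 this is 1.96 × √(0.0542/420) = 2.2 points.

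| Events | Majority rule | AUC 0.75 | Gain (points) | Paired half-width, n = 420 (points) |
|---|---|---|---|---|
| 10% | 90.0% | 90.1% | 0.09 | 0.7 (TP 0.0034, FP 0.0024) |
| 20% | 80.0% | 81.15% | 1.15 | 2.2 (TP 0.0329, FP 0.0214) |
| 40% | 60.0% | 69.8% | 9.8 | 5.3 (TP 0.2083, FP 0.1101) |

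At 10% and 20% events the gain is smaller than its half-width. At 40% it is clearly larger.

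**The case against.** A reader might infer three stronger points, and the documents support none of them.

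- **That models will be chosen on accuracy.** The text calls accuracy the first evaluation within a comparison on several metrics. It gives no ranking, weighting or selection rule, and list order is not priority. What stands is that the deciding metric is missing.
- **That useful and useless models would score almost the same.** This can be true of accuracy, and only for an unbalanced outcome. The plan also lists recall and AUC. At 20% events they read 0.16 and 0.75 for the model, against 0 and 0.50 for the majority rule. No event rate is given, and the abstract describes high mortality, so a rare outcome cannot be presumed. Stronger discrimination widens the gap too: AUC 0.90 at 20% events gives 87.3% against 80.0%.
- **That any miscalibration would pass unnoticed.** Doubling the risks themselves, rather than the logits, brings everyone with a true risk above 0.25 over the cut-off. At 20% events c becomes (0.455 + 1.386 − 1.099)/0.954 = 0.778, recall rises from 0.16 to 0.57, and accuracy falls to 0.2 × 0.570 + 0.8 × 0.782 = 73.9%. The listed metrics would move. The exact match in Step 2 belongs to distortions that leave each patient on the same side of the cut-off.

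Two limits on precision also apply. The half-width of a single accuracy estimate (3.8 points near 80% at n = 420) is the wrong yardstick for two rules applied to the same patients; the paired figure is smaller. And 420 is not stated to be a test-set size. If only 600 − 420 = 180 patients were available, the paired half-width at 20% events would be 3.4 points.

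The validation section's TRIPOD levels do not fill the gap. The protocol uses them to describe how data are split and whether external data are used, without naming a performance measure.

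**Conclusion.** The concern holds in limited form. The firm part is the missing calibration assessment. It rests on the text and on what the five metrics measure, and needs no particular event rate. A plan followed as written could pass a model whose individual risks are materially wrong: in the example, a mean of 11% against 20% observed, with all five metrics unchanged. That example assumes a binormal model, AUC 0.75, cut-off 0.5 and one form of overconfidence.

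The part on accuracy is conditional. Accuracy is a poor lead metric if the outcome is unbalanced (gains of 0.09 and 1.15 points at assumed rates of 10% and 20%) but informative near balance (9.8 points at 40%). Because other planned metrics would expose a majority-class model, this weakens the comparison without invalidating it. Overall this is an inexpensive improvement that the sponsor should make before modelling starts.

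**What to change.** In Predictive model development:
- Name the outcome and its expected rate.
- Make AUC with its confidence interval the lead measure of discrimination.
- Report accuracy, precision, recall and F1 as secondary, at a cut-off fixed in the training data, with the majority-class rate beside accuracy.

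In Predictive model validation:
- Add calibration intercept, slope and plot and the Brier score, in both internal and external validation.
- State that poor calibration counts as inadequate performance and sends a model back for retraining.

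The cost is some wording and a little more analysis of predictions already produced, with no new patients or data. Predicted probabilities must be kept as well as classes. Reported performance may look less favourable.

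### The aim is an accurate prediction model, but the only sizing is for an unnamed hypothesis test, and nothing ties 300 or 600 patients to the number of candidate predictors

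*Combined protocol and SAP*

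**What the plan says.** The Main objectives section sets the purpose: "The aim of LANTERN project is to develop accurate predictive models for lung cancer patients". The predictors come from five tiers. These include a DNA and RNA tumour panel (WP1) and four families of automatically extracted radiomic features (WP2). The number of candidate parameters is not stated.

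The Statistical Analysis Methodology section plans 600 patients and justifies them in one sentence: "Sample size was calculated on the basis of G-powerR program", with alpha 5% and power 90%. It gives no test, effect size, outcome, event rate, allocation, sidedness or dropout.

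Three smaller counts mark stages of the work: about 240 patients for feature identification (WP3), about 300 for development ("We estimate about 300 NSCLC cases with complete data to start developing the models") and about 420 for validation.

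Feature narrowing in WP3 draws on distributions, correlations and univariate analysis. The outcome-based part is explicit: "The Wilcoxon Mann-Whitney (WMW) test will be used to investigate the ability of these features to predict clinical outcomes on univariate analysis". Predictive model development then lists logistic regression and five machine-learning classifiers, with hyperparameters tuned by k-fold cross-validation. No penalty is named for the logistic model. Performance is judged by accuracy, precision, recall, F1 and AUC.

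**The concern.** Alpha and power size a test of one hypothesis. They do not say whether a model with many candidate predictors can be estimated well enough to predict in new patients. That depends on the number of candidate parameters, the outcome rate, the expected explained variation and the fitting method, and the plan links none of these to its patient numbers.

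What is at stake is the word accurate in the main aim. An overfitted model gives risks that are too high for high-risk patients and too low for low-risk ones. The listed metrics contain no calibration measure, so this could pass unnoticed, although the validation section ends with use in routine care.

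**Working it through.** **1. Can 600 be reproduced?** No, because no effect size is given. Working backwards for two equal groups, two-sided, and a difference in means in SD units:

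d = (1.960 + 1.282) × √(4/600) = 0.265.

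For the Wilcoxon Mann-Whitney test (relative efficiency 0.955), d = 0.265/√0.955 = 0.271. That is a single-feature AUC of Φ(0.271/√2) ≈ 0.58. Conventional effect sizes do not return 600: d = 0.2 needs 1,052 patients, 0.3 needs 468 and 0.5 needs 170. Whatever was entered, the result concerns one feature at a time.

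**2. How many candidate parameters do the patients support?** For a binary outcome and unpenalised regression with expected shrinkage S:

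p = n × (S − 1) × ln(1 − R2/S), with S = 0.90.

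From the plan: n = 300 and n = 600. Assumed: S and the Cox-Snell R2.

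| R2 | n = 300 | n = 600 |
|---|---|---|
| 0.10 | 3.5 | 7.1 |
| 0.15 | 5.5 | 10.9 |
| 0.20 | 7.5 | 15.1 |
| 0.30 | 12.2 | 24.3 |

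Example: 300 × (−0.10) × ln(1 − 0.20/0.90) = 300 × 0.10 × 0.2513 = 7.5.

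If R2 is instead derived from an event fraction of 10% to 50% and a C-statistic of 0.70 to 0.85, the range at n = 300 is 1.6 to 14.7. Ten events per parameter gives 3 to 15 over the same event fractions.

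In the other direction, at S = 0.90 and R2 from 0.30 down to 0.10, 30 parameters need about 740 to 2,550 patients, and 100 need about 2,470 to 8,490.

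**3. What would overfitting look like?** Simulated development sets of 300, about 30% events, five real predictors (log odds ratio 0.45 per SD, true AUC 0.74), all other candidates pure noise, unpenalised logistic regression, tested in new patients. Ranges are across repeated simulations:

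| Candidates | Apparent AUC | New-patient AUC | Calibration slope |
|---|---|---|---|
| 10 | 0.76 | 0.72 to 0.73 | 0.77 to 0.82 |
| 30 | 0.80 to 0.81 | 0.69 | 0.50 to 0.53 |
| 80 | 0.89 to 0.90 | 0.63 to 0.64 | 0.16 to 0.17 |

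A slope of 1 is ideal; below 1, predictions are too extreme.

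**4. Does a penalty cure it?** Largely, for the slope, when all candidates enter the fit. With cross-validated ridge the median slope is about 1.0 at 10 and 30 candidates and 1.10 at 80. At 30 candidates the new-patient AUC stays at 0.69.

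**5. Does it still cure it after outcome-based screening in the same patients?** No. Rank-based screening to 10 features, then refitting in the same 300:

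| Screened from | Slope, unpenalised | Slope, ridge |
|---|---|---|
| 100 | 0.53 | about 0.70 |
| 500 | 0.38 | 0.45 to 0.48 |

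The penalty acts only on the 10 survivors and cannot see the selection that came before it.

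**The case against.** Four counter-arguments carry weight.

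- **300 is a starting number.** The counts of 240, 300 and 420 each mark the start of a stage, and 600 are to be enrolled. A reader might infer that 300 is all the development data there will be; the text does not say so. The 600 column therefore matters too, although patients held out for testing keep the final development number below 600.
- **The plan does not say that the logistic model is unpenalised.** Hyperparameters are to be tuned, and plain logistic regression has none, so a tuned penalty is a plausible reading. A reader might infer that extreme predictions are certain. They are conditional on the fitting method, which the plan should state.
- **Noise-only extra features are a worst case.** If the extra features carry weak signal (log odds ratio 0.2 per SD, assumed), ridge on all 30 gives a new-patient AUC of 0.76 against 0.71 to 0.72 for 5 or 10 features; with 80 it is 0.78 against 0.66 to 0.67. Capping penalised models at the parameter counts above could then lower accuracy. The documents do not settle which case applies, so neither a hard cap on penalised models nor a blanket exploratory label for neural networks and boosted trees is justified.
- **Features will be narrowed, and models are modular.** Both help, and a parameter count would apply per module. But part of the narrowing uses the outcome, the plan does not keep screening patients apart from development patients, and the comprehensive avatar still combines the tiers.

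None of this supplies a sizing argument for the prediction aim.

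**Conclusion.** The point holds in this form: the patient numbers have no justification as numbers for a prediction model. That follows from the text alone.

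The size is conditional. About 4 to 12 candidate parameters at 300 and 7 to 24 at 600 rest on an assumed R2 of 0.10 to 0.30, shrinkage of 0.90 and no penalty; wider assumptions give about 2 to 15 at 300. That the planned predictors exceed these limits is inferred from the five tiers and the two high-dimensional panels, because no count is given. It is very probable, not documented.

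The more definite risk is the screening step. Outcome-based selection and model fitting in the same patients leave predictions too extreme even when the model is penalised, with the size in step 5 depending on the noise-feature assumption. The study remains feasible; the sponsor should make the change before modelling starts.

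**What to change.** 1. **Predictive model development:** specify a ridge or elastic-net penalty, tuned by cross-validation, for the logistic model.
2. **Feature selection (WP3 and Statistical Analysis Methodology):** reduce features within each tier without using the outcome, or repeat any outcome-based screening inside every cross-validation fold. Leave final selection to the penalised fit.
3. **Sample-size sentence:** stop presenting alpha 5% and power 90% as the basis for the prediction aim. State instead the expected shrinkage for the planned number of candidate parameters, and the expected width of the AUC confidence interval in the evaluation patients. Show both over a range of assumed outcome rates and R2.

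The cost is some extra analysis work and a less favourable sizing statement. No extra patients are needed.
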